## **Study Protocol**

Therapy will be administered to participants through a mobile application which all participants in the experimental group will use at home for two weeks. Before starting the use, pre-tests are conducted to determine the baseline scores of language function and communication using the Barcelona test and the Communicative Activity Log. In the introductory session, after the tests, the application is installed on the participant's own phone and the participant is given instructions and trained in how to use the application, before starting their individual use of it at home. The therapist will prescribe use of the application 2 times per day for 20 minutes. Support is made available during the two weeks, if the participant is having issues with the use of the application. Furthermore, all patients are informed that they are allowed to receive help from family members or others in using the application at home.

The participant is instructed to use the application two times every day for about twenty minutes, but although this was the recommended use, the participant is free to use the application when and for as long as they want. While using the app, the participant will, through the app, be informed when they have been practicing for twenty minutes, in order to limit their use to shorter but more frequent sessions. The practice consists of several different tasks that are connected to different contexts from everyday life. The tasks consist of matching visual objects, sounds, and short videos, as well as some written input of words. The tasks also ask participants to record their voice saying the name of the object and to listen to and evaluate their recording.

After two weeks, the participants will return and be given post-tests on the same measures as before the start of the treatment, i.e., clinical scales for assessing language function and communication. Additionally, they will complete two usability questionnaires (the System Usability Scale and the mHealth App Usability Questionnaire), and a few questions regarding risk assessment.

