## **Plan for Statistical Analysis**

The analysis of the Barcelona test and the Communicative Activity Log (CAL) will consist primarily of within-group analyses with the Wilcoxon rank sum test, because of the low number of subjects. Additionally, linear mixed effects models will be used for the between-group analyses, with the Barcelona Test and the CAL score for each domain (patient, family, and therapist), respectively, as the dependent variable. The main independent variable will be the pre-/post-test (time) through binary coding, as well as the control versus the experimental group, including the interaction between the time variable and the group. The participant ID will be included as random intercept in the model, to account for differences between participants. The validity of the regression analysis will be evaluated by testing the residuals of the model for normality using the Shapiro-Wilk test for normality. Given the low number of subjects, the descriptive statistics will be reported with medians and quartiles, as with non-parametric tests.

A descriptive analysis will be made of the SUS and MAUQ usability questionnaires to determine the potential of a mobile application by drawing general conclusions from the use of this specific application. These will be analysed with computation of overall scores and examination of scores of different qualities of the application and use.

Further analysis will consist of descriptive statistics of the use of the application, e.g., amount of use, reaction times, and recording length, for participants in the experimental groups. The variables will be checked for normality with the Shapiro-Wilk test and depending on the results either means and standard deviation or medians and quartiles will be reported. The use measures will be analysed with t-tests or Wilcoxon rank sum tests to evaluate whether they changed over time with the use of the application.

An additional analysis will be made of the score differences for the Barcelona test of the experimental group, where the amount of use will be included in a linear regression model. With the difference in test score as the dependent variable, the independent variables included will be the total amount of use of the application. This analysis will evaluate whether the amount of use influenced the outcome of the treatment.

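### App use is self-chosen, so regressing Barcelona change on total use describes an association and cannot meet the stated aim of showing influence

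*Combined protocol and SAP*

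**What the plan says.** In the Study Protocol, exposure starts from a target: "The therapist will prescribe use of the application 2 times per day for 20 minutes". The app also reminds users of the session length; they will "be informed when they have been practicing for twenty minutes, in order to limit their use to shorter but more frequent sessions". The target does not bind, because "the participant is free to use the application when and for as long as they want". Participants are also "allowed to receive help from family members or others in using the application at home".

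The last paragraph of the Plan for Statistical Analysis then says: "An additional analysis will be made of the score differences for the Barcelona test of the experimental group". The dependent variable is the pre-to-post difference, and "the independent variables included will be the total amount of use of the application". The purpose is stated as: "This analysis will evaluate whether the amount of use influenced the outcome of the treatment". The paragraph names no covariate, does not call the analysis exploratory or associational, and gives no caveat about use being chosen by the participant. No other section supplies one.

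**The concern.** The stated aim is causal, but the exposure is neither randomised nor fixed, and the model has one arm and one predictor. People who practise more may differ from those who practise less in severity, motivation or the help they actually receive. Someone who notices progress may also practise more, and the tasks have participants play back and judge their own recordings. These are plausible examples, not findings from the documents.

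What is at stake is how the result will be read. A positive slope could be reported as a dose-response effect of the app, and a flat one as evidence that the amount of practice does not matter. Either could instead reflect who chose to practise more.

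**Working it through.** The plan gives no sample size, significance level, expected slope or correlation for this analysis, so there is no figure to reproduce. The check is a reading of the design, followed by an illustration on assumed inputs.

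**1. Where the variation in use comes from.** The prescribed total is 2 × 20 × 14 = 560 minutes. If everyone used exactly that, no slope could be estimated. The slope rests entirely on differences in total use between participants, and the Study Protocol leaves those to the participants. The target and the twenty-minute notice may narrow the spread, but what remains is still self-selected.

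**2. What the slope estimates.** Let X be use and Y be change, each scaled to variance 1. The regression slope is cov(X, Y)/var(X).

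- Use affects change with coefficient β and nothing else is at work: slope = β.
- Use has no effect, and a common cause is correlated a with use and b with change: slope = a × b.
- Use has no effect, and improvement raises use (X = gY + noise): slope = g.

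Thus β = 0.25, a = b = 0.5 (0.5 × 0.5 = 0.25) and g = 0.25 all give the same slope. If the variables are also jointly normal, all three give the same joint distribution of use and change. Outside linear-normal models the distributions can differ, but the planned slope alone still does not show direction.

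Bias can also hide an effect. If Y = βX + cU + noise and X is correlated a with U, the slope is β + a × c. With β = 0.25, a = 0.5 and c = −0.5, it is 0.25 − 0.25 = 0.

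**3. Illustration.** All inputs here are assumed: no true effect of use, one unmeasured common cause, normal data, a two-sided 5% test and 10,000 simulated trials per cell. The Monte Carlo standard error is at most √(0.25/10,000) = 0.005.

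| a = b | expected slope | reject, n = 10 | n = 15 | n = 20 | n = 30 |
|---|---|---|---|---|---|
| 0 | 0 | 4.6% | 5.1% | 5.2% | 4.8% |
| 0.3 | 0.09 | 5.4% | 6.3% | 6.2% | 7.7% |
| 0.5 | 0.25 | 10.8% | 14.4% | 18.9% | 27.1% |
| 0.7 | 0.49 | 31.1% | 48.2% | 61.6% | 80.0% |

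The simulated mean slopes match the expected ones (0.088 to 0.093, 0.246 to 0.252 and 0.489 to 0.492). The bias does not shrink with n; a larger trial only detects it more often. At the weak end the rejection rate is close to nominal.

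For improvement raising use, rejection at n = 10 / n = 20 is 13% / 25% with g = 0.3 and 33% / 64% with g = 0.5 (40,000 trials per cell). This supposes that the whole two-week change feeds back into use. That is a strong assumption, because some use comes before some of the change.

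**4. Precision.** With use unrelated to change, the mean half-width of the 95% interval for the slope is about 0.81 SD of change per SD of use at n = 10, and 0.50 at n = 20. At such sizes a flat slope says little about whether use matters.

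**The case against.** The plan already keeps this analysis in its place. It comes last, is called additional, and no success criterion depends on it. The sentence states what will be evaluated, and its verb may be loose usage. The prescribed target, the in-app notice and the available support all pull use towards a common level. The named confounders are conjecture, and every number above is assumed.

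Most of this stands, and it is why the point is minor. It does not remove the problem. Additional is not the same as exploratory, the aim as worded is causal, and the remaining spread in use is chosen by the participant.

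A reader might infer more than the documents support:

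- *That the plan draws a causal conclusion.* It states an aim. The criticism is that the model cannot meet that aim.
- *That the slope will be biased, probably upwards.* The documents give no sample size or correlations, so neither the presence, the size nor the direction of bias can be established.
- *That the main comparisons are compromised.* Amount of use does not enter the planned within-group or between-group analyses of the test scores.
- *That adding the baseline Barcelona score would repair the analysis.* The score is available, since "pre-tests are conducted to determine the baseline scores of language function and communication using the Barcelona test". If baseline were the only common cause, adjustment would bring rejection back to about 5%. But if use follows true ability and the pre-test has error (assumed correlation 0.5, reliability 0.6), the planned model stays at about 5% while the adjusted one rejects 8% / 14% at n = 10 / 20. With an unmeasured cause at 0.5, both models give a mean slope of 0.25: they agree and are equally biased. Adjustment settles nothing here.

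**Conclusion.** The concern holds as a mismatch between a causal aim and a model that can only describe an association. It rests on two statements in the documents: participants choose their own amount of use, and total use is the only predictor in an analysis of one arm. It does not depend on the simulated figures, which show only that an apparent effect can arise when use has none, and that under weak confounding the distortion of the test can be negligible. Severity is minor, because the harm is limited to how this one additional analysis is interpreted.

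**What to change.** Replace the closing sentence of the Plan for Statistical Analysis with:

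*This exploratory analysis will describe whether the amount of use was associated with change in the Barcelona score; because use was self-chosen, it will not be interpreted as an effect of use.*

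Report the slope with its 95% confidence interval, so that a flat result from few participants is not taken as evidence of no relation.

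The cost is one reworded sentence and one interval. No new data, change to the intervention or change to the other analyses is needed. The downside is a more modest claim.
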